
#### Sensitivity analysis

A third category for group A "1.5 increase for study subjects with a baseline EDSS score of 0" shall only be used in a sensitivity analysis as performed in the SUNBEAM and RADIANCE trials.

#### **Power/Sample Size**

#### Primary objective

We want to show whether the correlation between the change in MS-related disability and the change in thalamic volume is different from zero. Both the change in MS-related disability and the change in thalamic volume are continuous variables. We will use Pearson's correlation analysis. The expected correlation coefficient is 0.15, which seems to be a reasonable assumption at this point because the correlation coefficient between change in MS-related disability and change in total brain volume published recently by Uher et al. (2021) is of the same order of magnitude.

Assuming a type I error of 0.05 and a type II error of 0.20, we estimate the required sample size to be 347 (24 months after baseline EDSS measurement). Considering an annual dropout rate of 15% the total required sample size is approximately 600 study participants.

## Secondary objectives

For addressing the secondary objectives groups 1 and 2 as defined in the statistical analysis methods are particularly relevant, but differences between all groups will be equally looked at. We assume an annual dropout rate of 15%. 24 months after baseline EDSS measurement study subjects shall be grouped based on their individual EDSS progress: group A comprises study subjects with (confirmed) disability progression and group B study subjects without disability progression. We assume that the incidence of study subjects in group 1 who belong to group A (with (confirmed) disability progression) is 5%. We further assume that the incidence of study subjects in group 2 who belong to group A (with (confirmed) disability progression) is 15%. The difference between groups 1 and 2 is significant (accepting a type-I error of 0.05 and a type-II error of 0.20) if the size of group 1 and group 2 is 196 and 98, respectively, 24 months after baseline EDSS measurement. Taking the annual dropout rate of 15% into account approximately 600 study subjects should be included.

The basic figures for incidence rates of disability progression in early MS patients for short and longer clinical trials were derived from Röver et al. (2015).

Similarly, we assume that 5% of patients in groups 2 and 3 (pooled) show disability progression between month 24 and month 36, whereas in group 1 the incidence is approximately zero. The difference between the pooled group and group 1 is significant (assuming a type I error of 0.05 and a type II error of 0.20) when the size of each of group 1 and the pooled group is 152.

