#### **Study Design:**

PENTAGON is a non-interventional, multicenter, prospective, observational study of active multiple sclerosis patients either already receiving or about to receive first-line oral therapy. Primary data will be collected for each study participant over a 24-month period. MS-related disability is characterized by the EDSS. The EDSS is determined at inclusion (baseline), 24 months after inclusion, and at additional visits at intervals of approx. every 6 months in between. Each study subject will undergo three brain MRI examinations using a standardized acquisition protocol following the 2021 MAGNIMS-CMSC-NAIMS consensus recommendations and including a high-resolution T1w MRI at affiliated radiology centers. The study will continue for an additional 12 months only if sample size requirements (minimum number of study patients at month 24) are met that indicate that the secondary outcome (S2) is sufficiently likely to be achieved. In a 6-month period preceding the primary data collection secondary data will be explored to confirm the validity of the statistical design and of the methodology.

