# (S2) To demonstrate that the change of thalamus volume during 24 months is predictive of the change of disability during the following 12 months (months 24-36).

We will build a statistical model based on clinical and MRI (estimated from three MRI measurements sampled at baseline (BL), at month 12 and at month 24) parameters to predict disability progression between month 24 and month 36. EDSS will be determined at additional visits at 30 and 36 months. The annual change of EDSS between months 24 and 36 will be determined by linear regression of EDSS versus time including 24, 30 and 36 months. The annual change of EDSS between months 24 and 36 will be dichotomized using the same predefined cutoff as deployed for (S1) (see above). The association between dichotomized disability change between 24 and 36 months and baseline (BL) parameters and TVL between baseline and 24 months will be tested using the chi-square statistic.

The following parameters will be used:

- Clinical scores / characteristics @ BL:
  - Age and sex

\_

<sup>1 Guideline on clinical investigation of medicinal products for the treatment of Multiple Sclerosis from EMA as of 26 March 2015

- disease duration (DD)
- EDSS
- Therapy
- MRI @ BL
  - z-scores of thalamus and whole brain volume
  - T2 lesion load
- MRI @ BL, month 12 and month 24
  - TVL and BVL

The model will be based on multivariate regression or support vector machines. The performance of the model will be characterized using a receiver operating characteristic (ROC) curve. The ROC will be evaluated with respect to accuracy, area under curve (AUC), sensitivity (true positive rate) and specificity (true negative rate). Within each classifier including both clinical and neuroradiological features, permutation importance will be calculated for each feature and for the random variable: only parameters whose importance are higher than the random variable's importance, will be considered as relevant in the classifier.

Baseline volumes for thalamus and whole brain will be estimated using a novel convolutional neural network-based approach, recently submitted for publication (Opfer et al. 2021).

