#### Overview patient attrition

| Timline                     | No of patients @
15% drop out
(annual) | Minimum No. of patients required to meet all endpoints | Sample size
requirement for
PE | Sample size
requirement for
S1 | Sample size
requirement for
S2 |
|-----------------------------|--|--|--------------------------------------|--------------------------------------|--------------------------------------|
| Baseline                    | 600  | >496   |                                      |                                      |                                      |
| Month 12                    | 510  | >422   |                                      |                                      |                                      |
| Month 24 (end of study)     | 433  | >358   | 347                                  | 392                                  |                                      |
| Month 36 (end of extension) | 368  | >304   |                                      |                                      | 304                                  |

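### The S2 sample size of 304 gives 80% power only with zero progression in group 1 during months 24 to 36, a rate the protocol does not justify against the 5% it assumes there for S1

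*Protocol*

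**What the plan says.** The Power/Sample Size section (Secondary objectives) carries two sets of progression rates.

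- **S1, baseline to month 24.** The "incidence of study subjects in group 1 who belong to group A (with (confirmed) disability progression) is 5" per cent. Group 2 is put at 15%.
- **S2, months 24 to 36.** Pooled groups 2 and 3 are put at 5%, "whereas in group 1 the incidence is approximately zero". With alpha 0.05 and beta 0.20, the protocol expects a significant difference "when the size of each of group 1 and the pooled group is 152".

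The S2 analysis section applies the S1 cutoff to the annual EDSS slope over months 24, 30 and 36. It states that the association with baseline parameters and "TVL between baseline and 24 months will be tested using the chi-square statistic".

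The patient attrition table enters 304 as the S2 requirement at month 36. Its column headed "Minimum No. of patients required to meet all endpoints" works back from there to more than 358 at month 24. The Synopsis makes the 12-month extension conditional on whether "sample size requirements (minimum number of study patients at month 24) are met", as a sign that S2 is sufficiently likely to succeed.

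**The concern.** Group 1 (normal whole-brain and normal thalamic volume loss) progresses at 5% over two years in one paragraph and at essentially nothing over the following year in another. No explanation is offered, and the one source cited for the rates is introduced for early MS in general.

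A zero rate is the most favourable value possible for a two-proportion calculation: for a given pooled-group rate it maximises the difference and removes all variance from one arm. If the true rate is small but not zero, the required number rises steeply.

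The figure also feeds a decision. The month-24 count that supports a further year of follow-up is derived from it. A sponsor who reads that count as 80% power could extend on a false premise and then take a null S2 result as evidence that thalamic volume loss does not predict disability.

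**Working it through.** **Inputs.** From Power/Sample Size: alpha 0.05, beta 0.20; S2 rates 0% and 5%; 152 per group; S1 rates 5% and 15% over 24 months; 15% annual dropout. From the attrition table: 304 required and 368 projected at month 36 (184 per group if split equally). Sidedness is not stated; the two-sided form reproduces the plan's figure.

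**Reproducing 152.** With p̄ the mean of the two rates,

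n = [1.960·√(2p̄(1−p̄)) + 0.8416·√(p₁(1−p₁)+p₂(1−p₂))]² / (p₂−p₁)².

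For 0% vs 5%, p̄ = 0.025: (0.4327 + 0.1834)² / 0.0025 = 151.9, so 152. The plan's number is right for its inputs.

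**Sensitivity to the group 1 rate.** The same formula solved for power is

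Φ{[(p₂−p₁)√n − 1.960·√(2p̄(1−p̄))] / √(p₁(1−p₁)+p₂(1−p₂))}.

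Example, 1% vs 5% at n = 152: (0.4932 − 0.4728)/0.2396 = 0.085, giving 53%.

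| Group 1 vs pooled 2+3 | Power, 152 per group | Power, 184 per group | n per group for 80% |
|---|---|---|---|
| 0% vs 5% (plan) | 80% | 87% | 152 |
| 0.5% vs 5% | 67% | 75% | 207 |
| 1% vs 5% | 53% | 61% | 285 |
| 2.5% vs 5% | 21% | 24% | 906 |
| 2.5% vs 7.5% | 52% | 60% | 298 |
| 2.53% vs 7.80% | 55% | 63% | 276 |

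The last two rows take both rates from S1. Simple halving gives 2.5% and 7.5%. A constant hazard gives 1−√0.95 = 2.53% and 1−√0.85 = 7.80%. Both rows give the pooled groups the group 2 rate, because the protocol states none for group 3. The 2.5% vs 5% row combines an S1-derived rate with an S2 rate, so it shows sensitivity and is not a consistent scenario.

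**Sparse table.** At 0% vs 5%, 152 × 0.05 = 7.6 events are expected in all, or 3.8 per group under the null, below the usual minimum of 5. With no events in group 1, the uncorrected chi-square is significant from 4 events in the pooled group (p = 0.044) and Fisher's test from 6 (p = 0.030). For a binomial with n = 152 and rate 0.05, the chance of at least 4 events is 95% and of at least 6 is 78%. The nominal 80% matches neither. Exact power (uncorrected chi-square, then Fisher) is 73% and 57% at 0.5% vs 5%, 54% and 40% at 1% vs 5%, and 56% and 45% at 2.53% vs 7.80%.

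**Link to the extension criterion.** 304/0.85 = 357.6, which is the month-24 entry of more than 358.

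**The case against.** **A reader might infer an arithmetic error.** There is none; 152 follows from the stated inputs.

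**A reader might infer that the protocol contradicts itself and that the true power is 21% to 55%.** The documents do not support this.

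- The windows differ, and so does the measure. S1 classifies the EDSS increase at month 24. S2 applies the cutoff to a slope over months 24, 30 and 36, which at equal spacing is simply the change from month 24 to month 36. A patient worsening steadily by 0.5 points a year reaches a 1.0-point rise for S1 but not for S2. A lower S2 rate is therefore plausible, and annualised S1 rates may be too high.
- The constant hazard and the group 3 rate are assumptions brought in from outside the protocol.
- The cited meta-regression might support period-specific rates; it cannot be checked here.
- Exact uncorrected chi-square power at 0% is 95%, and at 0.5% vs 5% with 184 per group it is about 81%.

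**A reader might infer that the extension would rest on a head count with no other check.** The Main phase milestones include a formal go/no-go (M-11), the start-up phase tests the design on secondary data, and the Synopsis calls the number of disabling events critical. S2 also plans a multivariable model with ROC evaluation, so it does not rest on the 2x2 table alone.

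**What stands.** The protocol gives no justification for zero, and the result depends on it. A lower S2 rate is not a zero rate, and at 1% vs 5% exact power is already 54% or less at 152 per group. M-11 states no event criterion. M-13 mentions events of 10% to 15%, but it falls due at month 48 after launch, after the extension has been run, and does not say whether the figure is cumulative; the S2 rates imply about 2.5% overall in months 24 to 36.

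**Conclusion.** The point holds as an unsupported assumption that sits uneasily with the S1 rates. By the formula behind the plan's figure, 80% power at 304 patients requires a group 1 rate of exactly zero. With the pooled groups at 5%, power drops to 67%, 53% and 21% at group 1 rates of 0.5%, 1% and 2.5%. On annualised S1 rates it is 52% to 55% at 304 and about 60% to 63% at the projected 368. Those last figures depend on the annualisation and on giving group 3 the group 2 rate, so they illustrate the fragility and do not estimate the real power. The more-than-358 criterion carries the same assumption.

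This should be fixed before the go/no-go. It is not critical to the study: S2 is a secondary objective in an optional extension, and the primary objective and S1 are unaffected.

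**What to change.** 1. Reconcile the S2 rates with the S1 rates or justify the difference, taking account of the 12-month window and the slope-based event, and state the rate assumed for group 3.
2. Replace the single statement that 304 gives 80% power with a table of S2 power for group 1 rates from, say, 0% to 2.5%, at 304 and at 368 patients. Do not substitute 55% or 63% as the new single answer; that would exchange one unsupported assumption for another.
3. Base the extension decision on that power, updated with the pooled progression rate observed in months 0 to 24, and not on the month-24 count alone. Enrolment runs from month 3 to month 12 after launch and M-11 falls at month 30, so only patients enrolled by month 6 will then have completed 24 months. The observed rate should be given with its uncertainty and with the conversion to a 12-month rate stated.
4. Use Fisher's exact test for the sparse 2x2 table. A Firth logistic regression on continuous thalamic volume loss is an option, not a requirement.

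The cost is a revised paragraph and table, one changed test, and probably a less favourable stated power. No patients, visits or scans are added.

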#### Overview patient attrition

| Timline                     | No of patients @
15% drop out
(annual) | Minimum No. of patients required to meet all endpoints | Sample size
requirement for
PE | Sample size
requirement for
S1 | Sample size
requirement for
S2 |
|-----------------------------|--|--|--------------------------------------|--------------------------------------|--------------------------------------|
| Baseline                    | 600  | >496   |                                      |                                      |                                      |
| Month 12                    | 510  | >422   |                                      |                                      |                                      |
| Month 24 (end of study)     | 433  | >358   | 347                                  | 392                                  |                                      |
| Month 36 (end of extension) | 368  | >304   |                                      |                                      | 304                                  |

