#### Main phase

Once ethics committee approval has been granted, enrollment of the first patients in the prospective observational study will begin. Enrollment of the first patients is planned 3 months after the official project launch. The enrollment period will last 9 months. Each study subject will be followed for 24 months. The EDSS is collected at inclusion (baseline), 24 months post baseline, and at additional visits at intervals of approx. every 6 months in between. Each study subject will undergo three brain MRI examinations using a standardized acquisition protocol following the 2021

MAGNIMS-CMSC-NAIMS consensus recommendations and including a high-resolution T1w MRI at affiliated radiology centers.

The following table provides checkmarks and / or milestones for the main phase including the extension period:

| ID   | checkmark / milestone description   | Type (mandatory / optional) | Due date (in
months after
official launch) |
|------|---|-----------------------------|--|
| M-8  | Launch of the prospective observational study at the investigator's own risk; first patient enrolled  | optional                    | +3   |
| M-9  | Last patient enrolled; baseline brain MRI examination (V1) for approx. more than 500 enrolled study subjects completed                                    | Mandatory                   | +12  |
| M-10 | V2 completed for approx. more than 430 enrolled study subjects  | Mandatory                   | +24  |
| M-11 | Interim analysis completed; formal go / no-go decision  | Mandatory                   | +30  |
| M-12 | V3 completed for approx. more than 350 enrolled study subjects  | Mandatory                   | +36  |
| M-13 | V4 completed for approx. more than 350 enrolled study subjects with an sufficient percentage number of disability events at a level of approx. 10% to 15% | Optional                    | +48  |

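### The attrition table's minimum for all endpoints is built from S2 alone, so its month-24 value (>358) is below the 392 that the same row requires for S1

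*Protocol*

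**What the plan says.** The table in section 4, Overview patient attrition, sets expected patient numbers at 15% annual dropout beside a column headed "Minimum No. of patients required to meet all endpoints" and one requirement column per endpoint. The month-24 row begins "Month 24 (end of study) | 433 | >358" and then gives 347 for the primary endpoint (PE) and 392 for S1. The only S2 entry is 304 at month 36. The other entries in the minimum column are >496 at baseline, >422 at month 12 and >304 at month 36.

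The S1 figure comes from Power/Sample Size, Secondary objectives. The contrast between groups 1 and 2 is said to be significant "if the size of group 1 and group 2 is 196 and 98, respectively, 24 months after baseline EDSS measurement". Section 4, Statistical Analysis Methods (S1), puts these groups at about 50% and 25% of patients. The S2 figure comes from the same power section, where the difference is said to be significant "when the size of each of group 1 and the pooled group is 152".

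The Main phase table in section 3 sets mandatory milestones of approximately more than 500 patients at baseline (M-9) and more than 430 at V2 (M-10). M-12 reads "V3 completed for approx. more than 350 enrolled study subjects". None of these mentions 392.

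**The concern.** A minimum that serves every endpoint cannot be smaller than the requirement of any one of them at the same time point. Here it is smaller by 392 − 358 = 34 patients, about 9% of 392. A study team steering by this column, or by the mandatory milestones, could report its numbers as sufficient for all endpoints while S1 is below the size that the protocol sets for it.

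**Working it through.** **Inputs (all from the protocol).** PE: correlation 0.15. S1: progression 5% in group 1 and 15% in group 2, sizes 196 and 98, shares of about 50% and 25%. S2: about 0% against 5%. Type I error 0.05, power 0.80, annual dropout 15%. The protocol does not state sidedness; two-sided testing reproduces its figures.

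**1. Reproduce the endpoint requirements.**
- PE, Fisher z: n = ((1.960 + 0.842)/atanh(0.15))² + 3 = 346.6, so 347. Agrees.
- S1, two proportions with 2:1 allocation, pooled variance under the null, no continuity correction. The pooled rate is (0.05 + 0.5 × 0.15)/1.5 = 0.0833. Then n₁ = [1.960 × √(3 × 0.0833 × 0.9167) + 0.842 × √(0.05 × 0.95 + 2 × 0.15 × 0.85)]² / 0.10² = (0.938 + 0.463)²/0.01 ≈ 196.3. The stated 196 and 98 agree within rounding. In total, (196 + 98)/0.75 = 392 exactly, so the 392 is no misprint.
- S2: 152 per group, 304 in all. Agrees.

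**2. Reproduce the minimum column.** Start from 304 at month 36 and divide by 0.85 per year:

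| Time | 304 back-calculated | Stated minimum |
|---|---|---|
| Month 24 | 304/0.85 = 357.6 | >358 |
| Month 12 | 304/0.85² = 420.8 | >422 |
| Baseline | 304/0.85³ = 495.0 | >496 |

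The match is within rounding, and S1 plays no part in it.

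**3. Minimum over all endpoints.** At month 24 it is max(347, 392, 358) = 392.

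| Time | Stated | All endpoints | Gap |
|---|---|---|---|
| Baseline | >496 | 392/0.85² = 542.6, so 543 | 47 |
| Month 12 | >422 | 392/0.85 = 461.2, so 462 | 40 |
| Month 24 | >358 | 392 | 34 |
| Month 36 | >304 | 304 | 0 |

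Month 36 stays at 304 because S2 is the only endpoint there.

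**4. What the milestones allow at month 24.** M-9: 500 × 0.85² = 361. M-10: 430 × 0.85 = 366. M-12: about 350 directly. All are below 392.

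**5. S1 power at those numbers.** Power = Φ((0.10 × √n₁ − 0.938)/0.55), where n₁ is half the total and 0.55 = √(0.0475 + 0.255).

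| Month-24 total | Groups 1 and 2 | Power |
|---|---|---|
| 433 | 216.5 / 108.25 | 83.4% |
| 392 | 196 / 98 | 79.9% |
| 358 | 179 / 89.5 | 76.6% |
| 350 | 175 / 87.5 | 75.8% |

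Exact enumeration of the uncorrected chi-square test gives 81.7% at 196/98, 77.6% to 78.6% at 179 with 89 or 90, and 77.7% at 175/88. The loss is again about 3 to 4 points.

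**The case against.** The best defence is that little depends on the error. The planned 600 gives 433 at month 24, where S1 power is about 83%. The primary endpoint's 347 is met at both 358 and 350. The milestones are approximate, and they do not copy the column: M-10 is above its 422 and M-12 below its 358. The 392 rests on group shares that are themselves approximate. The optional M-13 (more than 350 at V4) would imply about 350/0.85 = 412 at month 24. All of this stands and limits the consequence. It does not remove the contradiction within one table row, and no mandatory milestone secures 392.

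Three stronger readings are tempting, and the documents do not support them.

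- **That the extension decision is set too low.** The synopsis allows the extension "only if sample size requirements (minimum number of study patients at month 24) are met", but ties that condition to the prospects of S2. For S2, 304/0.85 ≈ 358 is the right month-24 count. S1 is assessed on month-24 data, so extending or stopping does not affect it.
- **That the decision falls before month 24 can be counted.** M-11 ("Interim analysis completed; formal go / no-go decision") is due at +30, and V3 completion only at +36. The protocol does not say that M-11 is the extension decision. Its synopsis wording would allow a projected count, and any figure for patients past month 24 at +30 needs an accrual pattern that is not stated.
- **That 600 is itself too few at 20% dropout.** That would leave 600 × 0.80² = 384. The synopsis gives the 15% to 20% range for the primary objective, whereas S1 and the table use 15%. Even at 384, the same formula gives S1 power of 79.2%.

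**Conclusion.** The month-24 minimum is wrong as labelled: it should be 392, not 358, and the month-12 and baseline entries are too low by 40 and 47. The mandatory milestones share the gap. If attrition or recruitment falls short of plan, S1 could run at about 76% to 77% power by normal approximation instead of 80%, while every mandatory threshold is reported as met. This assumes 15% annual dropout, group shares of 50% and 25%, and a two-sided test without continuity correction. Planned enrolment is adequate under those assumptions, and neither the primary endpoint nor the S2 extension count is affected. The point should be fixed, but it does not threaten the study.

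**What to change.** Either of two wording changes resolves it.

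1. Restate the minimum column as ≥543 at baseline, ≥462 at month 12, ≥392 at month 24 and ≥304 at month 36, and align M-9, M-10 and M-12 with the first three.
2. Keep the figures, relabel the column as the minimum for the primary endpoint and S2 only, and state that S1 power is about 77% at 358.

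Under either option, the extension condition should stay on S2's own requirement, about 358 at month 24. Raising it to 392 could cancel a viable S2 extension without helping S1. The cost is an edit to the table, plus the milestone wording under the first option. No extra enrolment is needed, since 600 × 0.85² gives 433. The downside of the first option is slightly stricter mandatory milestones.
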